**1. LIST OF ABBREVIATIONS AND DEFINITIONS OF TERMS:**

| Abbreviation | Definition                                   |
|---------------------|---|
| AE                  | Adverse Event(s)                                    |
| AF                  | Anchoring Fibrils                                   |
| ALT                 | Alanine Transaminase                                |
| AST                 | Aspartate Transaminase                              |
| BSA                 | Body Surface Area                                   |
| BUN                 | Blood Urea Nitrogen                                 |
| CBC                 | Complete Blood Count                                |
| CFR                 | Code of Federal Regulation                          |
| cGMP                | Cyclic Guanosine Monophosphate                      |
| cm      | Centimeters squared or square centimeters (area)    |
| CPK                 | Creatine Phosphokinase                              |
| CRF                 | Case Report Form                                    |
| CT                  | Computed Tomography                                 |
| CYP3A               | Cytochrome P 450 3A                      |
| DSMB                | Data Safety Monitoring Board                        |
| EOS                 | End of Study  |
| EOT                 | End of Treatment                                    |
| FDA                 | Food and Drug Administration                        |
| GCP                 | Good Clinical Practice                              |
| HIPAA               | Health Insurance Portability and Accountability Act |
| Hgb                 | Hemoglobin  |
| IB                  | Investigator's Brochure                             |
| ICH                 | International Conference on Harmonization           |
| IEC                 | Independent Ethics Committee                        |
| IND                 | Investigational New Drug                            |
| IRB                 | Institutional Review Board                          |
| IUD                 | Intrauterine Device                                 |
| LDH                 | Lactate Dehydrogenase                               |
| LM                  | Lymphatic Malformation                              |
| N/A                 | Not Applicable                                      |
| MCV                 | Mean Corpuscular Volume                             |
| MCH                 | Mean Corpuscular Hgb                                |
| MCHC                | Mean Corpuscular Hgb Concentration                  |
| MRI                 | Magnetic Resonance Image                            |
| RBC                 | Red Blood Cells                                     |
| RDW                 | RBC distribution width                              |
| SAE                 | Serious Adverse Event(s)                            |
| SMP                 | Safety Monitoring Plan                              |
| SOP                 | Standard Operating Procedures                       |
| UP                  | Unanticipated Problems                              |
| UPT                 | Urine Pregnancy Test                                |
| WBC                 | White Blood Cells                                   |

## 2. SYNOPSIS

Study Phase: 2

Financial Disclosure Information for U.S. FDA Submission to be Obtained? Yes

Test Medication: Sildenafil 20 mg tablets, 2.5mg/ml suspension (Revatio®)  
Control Medication: Placebo tablets or suspension resembling Revatio®

Study Dosage / Usage: Oral dosage of sildenafil. For pediatric patients 8 kg to 20 kg the suspension/tablets dose will be 10 mg/4ml three times a day (30 mg per day) and for patients > 20 kg the dose is 20 mg/8ml three times a day (60 mg a day). Subjects less than 8 kg will not be enrolled in the trial.

Route of Administration: The medication will be given orally. The subjects who will receive the 10 mg dose will be given an oral suspension (using dose calculation by the study pharmacist) or half a tablet. Subjects will have the option of taking tablets or receiving an oral suspension of the medication in 2.5mg per mL.

Objective(s): The objectives of this study are to assess the safety and effectiveness of sildenafil taken orally to improve or resolve lymphatic malformations.

Study Population: Sixty Subjects (60)

Subjects will be between the ages of 6 months to 10 years of age inclusive with lymphatic malformations (LM) that have a **minimum diameter of 3 centimeters** based upon MRI evaluation. Based on the patient numbers in pediatric dermatology clinics over the country, we expect that we will be able to screen 60 patients who will meet the inclusion criteria, and 55 patients will be enrolled in the study and begin medication. After 15 subjects are completed, an interim analysis will be performed to project effect size and estimate the total number of subjects required for the study. If after analysis of 15, 30 or 45 subjects we find that we are in the range of futility or efficacy, then we will notify the FDA as well as the DSMB, and begin to end the study by adding no additional subjects.

Structure: Double-blind trial of placebo compared to sildenafil with an open label extension for subjects who received placebo. Two to one ratio of two sildenafil treated subjects who

receive active sildenafil to one placebo treated subject. During the twenty week evaluation visit, after completion of all evaluations, the randomization code will be broken and both the subject and investigator will know the results. The subjects who have randomized to placebo will have the option to begin a twenty week course of sildenafil. If the subjects who were on placebo elect to take active drug, the initiation visit can be completed at that time. The subject will then be followed with clinic visits at weeks 4, 12, 20 and 32 as indicated in the protocol. We will call the subjects at weeks 2, 8 and 16 to inquire about any questions that the subjects may have or any concerns. We will also request information on medication taken and their progress.

The subject's LMs will be categorized by the Pediatric Radiologist by the percent of the LM that is microcystic. Upon completion of the initial 15 subjects, the data will be evaluated in an interim analysis in order to determine if the percent of macrocystic component of the lesions suggests which subjects may have the best benefit. The initial 15 subjects will also be evaluated related to previous procedures, infections and other complications related to their lymphatic malformations. If specific characteristics of the LM are identified that suggests beneficial effect of the sildenafil, the protocol will be changed to enroll those subjects who are projected to have the best benefit. A new power analysis will be done to project the minimum numbers of subjects that should be enrolled further in the study.

Duration of Treatment: 20 weeks. Placebo subjects will complete 20 weeks of placebo and then have an option for 20 weeks of active sildenafil.

Duration of Assessment: The subjects will be evaluated for 20 weeks on therapy then followed for 12 weeks off therapy.

Open Label Extension: Placebo subjects will have an option to enter an open label treatment after they have completed 20 weeks of placebo.

Duration of treatment: Placebo 20 weeks  
Washout Between Periods: none  
Duration of Treatment: 20 weeks on active drug

After the completion of 20 weeks of sildenafil and 12 weeks of follow up, the subjects will have the option to be followed through an IRB approved long-term follow up trial not

covered in this IND application. That IRB trial would allow up to five years follow up on subjects and would only allow investigators to observe how the subject is doing long term, whichever treatment options the subject pursues in consultation with their regular doctor in that time. That planned follow up protocol will allow Stanford to contact the subjects several times a year in order obtain information about any therapy they may elect to follow, including sildenafil if their regular doctor prescribes it, and their response to any therapy.

Multi-Center:

Yes

Number of Centers:

Up to 4

Blinding:

|                |     |
|----------------|-----|
| Observer-Blind | Yes |
| Subject-Blind  | Yes |
| Double-Blind   | Yes |

Randomization:

Group Assignment Ratio: 2:1 randomization of two subjects who receive sildenafil to one subject who receives placebo.

Concurrent Control:

No other treatments for lymphatic malformation will be allowed except antibiotics and/or surgical drainage if the lesions become infected. Treatment for recurrent infections in the lymphatic malformation will be allowed and documented during the trial. Concurrent medications will be documented. Subjects who require sclerosing agents or excisional surgery of their lymphatic malformation will be withdrawn from the trial.

Variable(s): PRIMARY: Change in lesion volume over twenty weeks of the test medication as evaluated by MRI examination. Comparison of placebo to sildenafil treated subjects.

SECONDARY: Change in lesion volume estimated using a soft tape measure to measure the length, width, and hemispheric measurement of each of the lymphatic malformations. (Berk, Berk et al. 2011) Completion of the form *Lymphatic Malformation Measurements*.

Subject's evaluation of the change in lesion clinical characteristics from baseline to 20 weeks by examining decreased discomfort, texture or thickness, distortion of normal anatomy or overall change obtained in the subject's

completion of *Subject's Assessment of Lymphatic Malformation Change* form.

Physician's evaluation of the lesion clinical characteristics on the day of the visit. This includes color, tenseness and texture, superficial component, deep component, and distortion of anatomical landmarks. This requires completion of the *Lymphatic Malformation Assessment* form for each LM site.

Physician's evaluation of the change in lesion clinical characteristics from baseline, such as change in texture or thickness, change in distortion of normal anatomy, and over change in lesions. This requires completion of the *Lymphatic Malformation Assessment of Change* form for each LM site.

Comparison of LM volume from MRI assessment to Body Surface Area (BSA) measurements before and after 20 weeks of sildenafil.

Blinded physician observer scored evaluation of clinical photographs taken prior to the initial dose of sildenafil or placebo and at the 20 week visit prior to the unblinding. Subjects who receive placebo and then enter the 20 week open label continuation will have additional photographs taken after 20 weeks of sildenafil.

Presence, frequency or absence of infection during trial.

Relationship of response to sildenafil to previous infections, sclerotherapy or surgery.

**SAFETY:** Adverse events and frequency of lesion infections.

Adverse Events: Both volunteered and elicited.

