### **3.3. OBJECTIVE**

The objective in this study is to assess the safety and efficacy of sildenafil in reducing the volume and symptoms of lymphatic malformations when administered to subjects who have lymphatic malformations greater than 3 cm in diameter.

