## 5.2. INCLUSION CRITERIA

Subjects will be considered qualified for enrollment if they meet the following criteria:

1. Legally authorized representative of subjects willing and able to give consent. Assent will be obtained for subjects between the ages of 7 and 10 years old.
2. Subjects will need to be 6 months of age to 10 years of age at the time of entry into the study.
3. The minimum weight of a subject will need to be 8 kg at the time of enrollment.
4. Subjects will be required to have the clinical diagnosis of lymphatic malformation that appears to be over 3 cm in greatest diameter in order to be evaluated for entry. A review of a previous MRI examination may help confirm the entry criteria on subjects selected to come to Stanford for the MRI screening. The MRI must be performed within six (6) months of the screening visit if used as a baseline measure.
5. The lymphatic malformation should be causing enough disability for the subject requiring them to consider systemic therapy.
6. Females must not be pregnant or breast-feeding.
7. Female subjects of childbearing potential have negative urine-pregnancy test results.
8. A parent or legally authorized representative must be willing and able to ensure subject is present for all required study visits.
9. A parent or legally authorized representative must be able to follow instructions.
10. During the initial screening evaluation portion of the trial the subjects MRI examination will be required to confirm that the lymphatic malformation is present and is greater than 3 cm in diameter in order for the subjects to receive medication. MRI of less than six months is valid to use during screening with the discretion of the study radiologist.
11. Subjects will have no contraindications for the use of sildenafil.
12. Subjects will have a normal eye examination.
13. Subjects will have normal liver and kidney function.
14. Subjects will have no contraindication to MRI examinations such as metal implants, etc.
15. Subject must not be a smoker.

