#### **7.1.3. Baseline Study [Day 0 (medication dispensed)] at Stanford**

This will usually be the day after the screening.

1. Review inclusion and exclusion criteria with the subject, including the results of their laboratory data, eye examination, and MRI. If subject no longer meets criteria for participation, exit the subject from the study as a screen failure.
2. Obtain demographic information and medical history, including information on all medications currently being taken. Document concomitant medications. Instruct the subject and/or caregiver of the excluded medications and give them a list if they do not have their list that was previously given to them.
3. Perform a physical examination including heart and pulmonary auscultation, liver and spleen palpation, abdominal auscultation and palpation, and documentation of

peripheral pulses. Examine and describe the characteristics of their lymphatic malformation to see that it meets the criteria for the trial.

4. Obtain Vital Signs including height, weight, temperature, heart rate, blood pressure, respiratory rate, and oxygen saturation.
5. Clinical assessment of each lymphatic malformation including measuring the hemicircumference of the lesion by using a soft measuring tape placed on the skin over the area of the widest diameter of the lesion. The length, and width, will then be calculated as described in Figure 2 of Berk et al.(Berk, Berk et al. 2011) In order to document the site of the measurements a diagram will be drawn by hand or photographs will be taken of the methods. Each clinic visit will try to duplicate the measurements methods used in the initial visit.
6. Physician's evaluation of the lesion clinical characteristics on the day of the visit. This includes color, tenseness and texture, superficial component, deep component, and distortion of anatomical landmarks. This requires completion of the *Lymphatic Malformation Assessment* form for each LM site.
7. Site investigator will acquire digital photographs of each lymphatic malformation as described in Section 7.4.4, and summarized as follows:
  - Subject will be seated on a chair. If subject is an infant, then subject's parent or guardian will be seated on a chair with subject sitting on his/her knees or in his/her arms.
  - All photographs will include a color chart in the field of view, held in the same plane as the target lymphatic malformation.

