7. Clinical assessment of each lymphatic malformation including measuring the hemicircumference of the lesion by using a soft measuring tape placed on the skin over the area of the widest diameter of the lesion. The length, and width, will then be calculated as describe in Figure 2 of Berk et al (2011). In order to document the site of the measurements a diagram will be drawn by hand or photographs will be taken of the methods. Each clinic visit will try to duplicate the measurements methods used in the initial visit.
8. Completion of subject's evaluation of the change in lesion clinical characteristics from baseline, such as decreased discomfort, texture or thickness, distortion of normal anatomy or overall change obtained in the subject's completion of *Subject's Assessment of Lymphatic Malformation Change* form.
9. Completion of the physician's evaluation of the lesion clinical characteristics on the day of the visit. This includes color, tenseness and texture, superficial component, deep component, and distortion of anatomical landmarks. This requires completion of the *Lymphatic Malformation Assessment* form for each LM site.
10. Physician's evaluation of the change in lesion clinical characteristics from baseline, such as change in texture or thickness, change in distortion of normal anatomy, and over change in lesions. This requires completion of the *Lymphatic Malformation Assessment of Change* form for each LM site.
11. Count study drug and perform compliance assessment; medication journal reviewed.

12. Study medication dose will be calculated based upon the weight of the subject during the visit. The Stanford site will be notified of the weight and dose. The Stanford physician will notify the pharmacy of the subject number and proposed dose. The Stanford pharmacy will dispense adequate study medication (sildenafil or placebo) to last until the next visit. The medication will be shipped directly to the subject's home.
13. Review possible adverse events included in informed consent.
14. New medication journals reviewed and instructions reviewed.
15. Arrange a MRI examination to be done before the 20 week visit at Stanford.
16. Instruction sheet will be given to the subjects documenting contact information for the research physicians and excluded medications and foods while on sildenafil if they do not have the instruction sheet previously given to them.

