## 16. STUDY PLAN

Table 16-1: Study Procedures by Treatment Day

| Visit:  | Screening
(Day -7 to +1) | Baseline &
Baseline-A 
(Day 0) | Week 2 &
Week 2-A 
(~4 1 Day) | Week 4  &
Week 4-A 
(~4 14 Days) | Week 8 &
Week 8-A 
(~4 1 Day) | Week 12  &
Week 12-A 
(~4 14 Days) | Week 16 &
Week 16-A 
(~4 1 Day) | Week 20 &
Week 20-A 
(~4 14 Days) | End of Study 
Early Exit 
(Week 32)
(~4 14 Days) |
|---|-----------------------------|--|---|--|---|--|---|---|---|
| Procedures:                            |                             |  |   |  |   |  |   |   |   |
| Informed Consent/Accent                       | x                           |  |   |  |   |  |   |   |   |
| Inclusion/Exclusion criteria                  | x                           |  |   |  |   |  |   |   |   |
| Vital signs (height, weight, HR, BP, temp)    | x                           | x  |   | x  |   | x  |   | x   | x   |
| Complete history                              | x                           |  |   |  |   |  |   |   |   |
| Interval history                              |                             | x  | x   | x  | x   | x  | x   | x   | x   |
| Physical examination                          | x                           | x  |   | x  |   | x  |   | x   | x   |
| Phone call                                    |                             |  | x   |  | x   |  | x   |   |   |
| Assessment of LM by MD                        | x                           | x  |   | x  |   | x  |   | x   | x   |
| Assessment of LM by participant               |                             |  |   | x  |   | x  |   | x   | x   |
| LM measurements                               | x                           | x  |   | x  |   | x  |   | x   | x   |
| LM photographs                                | x                           | x  |   | x  |   | x  |   | x   | x   |
| Laboratory tests                              | x               |  |   |  |   |  |   | x   |   |
| Urine pregnancy test                          | x               |  |   |  |   |  |   | x                                       |   |
| Ophthalmology exam                            | x               |  |   |  |   |  |   | x                                       |   |

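### Discomfort is rated by the family only as change from baseline, with no scheduled rating before the first dose, so the discomfort item loses sensitivity among children who had none at entry

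*Combined protocol and SAP*

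**What the plan says.** Section 3.3 sets out to "assess the safety and efficacy of sildenafil in reducing the volume and symptoms of lymphatic malformations". Among the rated efficacy variables in the Synopsis and Section 10.2.2, discomfort appears in one place, the family's form on change: "Subject's evaluation of the change in lesion clinical characteristics from baseline to 20 weeks by examining decreased discomfort, texture or thickness".

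The visit sections use the same wording. At Weeks 4 and 12 (7.1.5) the step is "Completion of subject's evaluation of the change in lesion clinical characteristics from baseline, such as decreased discomfort, texture or thickness, distortion of normal anatomy", and 7.1.6 (Week 20) and 7.1.7 (Week 32) repeat it. In Table 16-1 the row "Assessment of LM by participant" is marked at Weeks 4, 12, 20 and End of Study. It is blank at Screening and Baseline.

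The lesion form completed at Baseline belongs to the physician: "Physician's evaluation of the lesion clinical characteristics on the day of the visit". Its listed content is: "This includes color, tenseness and texture, superficial component, deep component, and distortion of anatomical landmarks". No pain or discomfort item is listed.

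Entry requires burden but not discomfort: "The lymphatic malformation should be causing enough disability for the subject requiring them to consider systemic therapy" (5.2, item 5). Medical history is taken at Screening and Baseline, and 7.4.1 records associated complications, giving infection and disability as examples. Section 10.2 evaluates all dosed subjects for efficacy. Section 10.2.2 gives no baseline symptom covariate, symptomatic subset or rule for children to whom the item does not apply.

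**The concern.** A child who has no discomfort when treatment starts cannot report less of it later. If the starting level is not recorded, that child looks the same as a child who had discomfort and did not improve. Both arms then contain children who could not respond on this item, and the visible difference shrinks in proportion to their share. Section 3.1 says that extremity lesions are painful only at times, so such children are to be expected, though no proportion is given.

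The rating also asks the family to compare the present with an unrecorded state, about 20 weeks back at the Week 20 visit. The physician, by contrast, has a current-status form at Baseline as well as a later change form. The plan therefore records a starting level for the features the physician rates but schedules none for discomfort.

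At stake is the ability of a trial of at most 60 children to see a real effect on the one discomfort measure that it has.

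**Working it through.** **Reading the schedule.** Four places were set side by side.

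| Place | Family rating of discomfort |
|---|---|
| Screening (7.1.2; Table 16-1) | none |
| Baseline (7.1.3; Table 16-1) | none |
| Weeks 4, 12, 20 (7.1.5, 7.1.6; Table 16-1) | change from baseline |
| Week 32 (7.1.7; Table 16-1) | change from baseline |

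Baseline Active (7.1.8) follows 7.1.3, so the open-label period has the same gap.

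**No planned figure to reproduce.** Section 11 sets 60 subjects by availability and says that no effect size can be developed. No alpha, power or response rate is stated.

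**Illustration.** From the documents: 60 subjects at 2:1, so 40 v 20. Assumed:
- the item is reduced to improved or not, and tested by a two-sided 5% Fisher test;
- among children with discomfort at entry, improvement is 70% v 20%, or alternatively 50% v 20%;
- a share f has no discomfort at entry and cannot improve, with f = 25%, 50% or 60%.

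All children: the rates become p(1 − f) in each arm, so the visible difference is (p_T − p_C)(1 − f). With 70% v 20% this is 50 × 0.75 = 37.5, 50 × 0.50 = 25 and 50 × 0.40 = 20 points.

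Symptomatic children only: the rates stay at p, but the arms shrink to 40(1 − f) v 20(1 − f), that is 30 v 15, 20 v 10 and 16 v 8.

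Power is the sum, over all pairs of counts with Fisher p ≤ 0.05, of the product of the two binomial probabilities.

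| f | 70% v 20%: all children | symptomatic only | gain (points) | 50% v 20%: all children | symptomatic only | gain (points) |
|---|---|---|---|---|---|---|
| 25% | 80% | 88% | 8 | 38% | 42% | 3 |
| 50% | 52% | 66% | 14 | 23% | 27% | 4 |
| 60% | 40% | 59% | 19 | 16% | 19% | 3 |

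Gains are taken before rounding.

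**What the missing rating accounts for.** With 70% v 20% and f = 0, power is 95%. At f = 60% it is 40%, a loss of 95 − 40 = 55 points. Restricting to symptomatic children returns 59 − 40 = 19 of these. The other 95 − 59 = 36 points come from having fewer children with discomfort, which no form can change.

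**Fewer completers.** Section 5.1 sets a goal of 40 completers. At 27 v 13 with 70% v 20%, the all-children figures are 60%, 29% and 19%, and the restricted figures are 66%, 51% and 39% (arm sizes rounded to whole children).

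**The case against.** The case on the other side has several parts, and most of them limit the point.

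- The change form is not reproduced, and the visit sections introduce its items as examples. It could hold an option for no discomfort at baseline, which would separate the children. None is described, but it cannot be excluded. Such an answer would still be given after dosing and would not be a baseline measurement.
- A reader might infer that no baseline information exists and that the gap can never be repaired. The documents do not support that. Medical history is taken twice before the first dose, the list of complications in 7.4.1 is open, and item 5 of 5.2 makes the investigator judge the child's burden. Whether discomfort was present may be recoverable from source records for some children. What is absent is a scheduled, structured rating.
- The plan defines no responder test on discomfort. It is one item beside texture or thickness, distortion and overall change, on one of several secondary variables, in a study that Section 11 calls exploratory and descriptive. The floor shown here applies to the discomfort item only.
- Infection, which Section 3.1 names among the morbidities, is a separate endpoint, so discomfort is not the only measure of burden.
- Recall is an inference. The form is also completed at Weeks 4 and 12, and under blinding and randomisation recall error adds noise and does not by itself favour an arm.
- Many children are too young to rate themselves, so a baseline rating would often be by proxy. This stands as a limit on any family rating.

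These arguments reduce the size and certainty of the point. They do not supply the missing rating: neither 7.1.3 nor Table 16-1 schedules one, and 10.2.2 describes no way to identify children without discomfort at entry.

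**Conclusion.** The point holds as a cheap improvement to one item of a secondary variable. Symptom reduction is an objective, discomfort is listed only on a change form, and no structured family rating before the first dose is scheduled. Subject to what the unseen form and the history contain, children without discomfort at entry cannot be separated from symptomatic children who did not improve.

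The effect is lower sensitivity. It does not bias the randomised comparison, does not in itself raise the false-positive rate, and leaves the MRI primary untouched. A reader might take the whole fall in power from 95% to 40% as the price of the omission. It is not: in that case the rating returns 19 of the 55 points.

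Across the assumed cases the gain is about 8 to 19 points of power at 70% v 20%, and about 3 to 4 at 50% v 20%. These figures rest on assumed response rates, an assumed share without discomfort and an assumed binary test. They illustrate the direction and the range and do not estimate this trial's power. The gain from a baseline-adjusted comparison of ratings was not calculated.

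**What to change.** - **Section 7.1.3 and the Baseline column of Table 16-1:** add one family rating of the child's current discomfort, with none as an allowed answer, completed before the first dose and by proxy where the child cannot answer.
- **Sections 7.1.5, 7.1.6 and 7.1.7, and Table 16-1:** repeat the same item at Weeks 4, 12, 20 and 32.
- **Section 10.2.2:** compare arms at Week 20 on this rating adjusted for its Baseline value, and report decreased discomfort among children who had discomfort at Baseline.

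Keep the change form. Family status ratings of texture or distortion need not be added, because the physician already rates these at Baseline.

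The cost is a few minutes at visits that already take place, plus edits to the form, the table and one analysis paragraph. Ratings in young children will be by proxy, and children already enrolled will have no Baseline rating.
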